9. STUDY TREATMENT

9.1. Description of Study Treatment

AG-120 will be administered orally at a dose of 500 mg (provided as 250 mg strength tablets). Placebo will be supplied as matched tablets to be administered orally.

9.2. Study Treatment Packaging and Labeling

AG-120 and matched placebo will be supplied in appropriate containers with child resistant closures and will be labeled appropriately as investigational product for this study.

Packaging and labeling will be prepared to meet all regulatory requirements.

9.3. Study Treatment Storage

AG-120 tablets and matched placebo tablets must be stored according to the package label.

All study treatment products must be stored in a secure, limited-access location and may be dispensed only by the Investigator or by a member of the staff specifically authorized by the Investigator.

9.4. Method of Assigning Subjects to Treatment

Subjects who meet all study eligibility criteria will be randomly assigned in a 2:1 ratio, stratified by number of prior systemic treatment regimens for advanced disease (1 or 2), to receive AG-120 orally QD or AG-120-matched placebo orally QD.

The randomization schedule will be generated by an independent statistical group. The randomization assignment will be implemented by an interactive web response system (IWRS).

9.5. Blinding

The subjects, Investigators, the clinical research unit staff who deal directly with subjects, and the Sponsor will be blinded to study treatment assignment until documented disease progression. The IWRS will assign each subject specific Medication ID-labeled study drug containers. AG-120 and placebo will be packaged and labeled identically so that the study pharmacist will remain blinded to treatment assignment.

The subjects, clinical research unit staff, and Sponsor will remain blinded for the duration of the study unless emergency unblinding is required (see Section 9.6). Upon request by the Investigator, subjects and staff will be unblinded at the time of disease progression as confirmed by study sponsor.

An IDMC will review unblinded safety and other clinical data at scheduled meetings; the unblinded summaries will be prepared by an independent statistical center (Section 10.5.1).

9.6. Unblinding

The need to unblind study treatment should first be discussed with the Sponsor's Medical Monitor (or Responsible Medical Officer), if at all possible. In the event of a medical emergency

or pregnancy in a female subject or in the sexual partner of a male subject, in which knowledge of the investigational product is critical to the subject's management, the study treatment may be unblinded for that subject by the treating Investigator. Investigators are encouraged to discuss a plan to break the blinding code with the Medical Monitor.

In case of an emergency, the Investigator may access the IWRS to reveal the identity of the treatment for that subject. Once the decision to unblind has been made, the Investigator must record the nature of the emergency that required the unblinding, along with the date and time of the unblinding on the proper source documentation and notify the Sponsor's Medical Monitor (or Responsible Medical Officer) of the unblinding.

In the event that a subject's treatment assignment is unblinded, either accidentally or in the case of emergency unblinding, the subject will be allowed to continue study treatment. In the case of emergency unblinding, if the subject is receiving placebo, cross over to AG-120 will not be permitted until documented progression.

Upon request by the Investigator, the subject and site staff will be unblinded to treatment assignment after documented disease progression (as assessed by the Investigator and after consultation with the Sponsor Medical Monitor), and subjects randomized to the placebo arm who still meet eligibility criteria will be given the opportunity to cross over to the active treatment arm and receive AG-120. For those subjects who cross over, placebo will not be counted as a prior line of therapy for the purpose of eligibility. If subjects cross over, they will follow the same assessment schedule as from C1D1. These subjects will continue to be evaluated for tumor response by the Investigator. If the treatment assignment is determined to be AG-120 upon radiographic disease progression, the Investigator may consider continuing AG-120, provided the subject appears to be clinically benefitting and there is no contraindication to continuing treatment beyond progression (see Section 9.8 for parameters for treating beyond progression).

Palliative radiotherapy to treat symptomatic non-target lesions per RECIST v1.1 that cannot otherwise be medically managed will be permitted after disease progression has been verified and unblinding has occurred (see Section 9.8.1.3). AG-120 should be held for the duration of palliative radiotherapy. Palliative radiotherapy and any other anti-cancer therapy will not be permitted during the blinded portion of this study. Any decision to pursue palliative radiotherapy will require Medical Monitor approval. After palliative radiotherapy, there will be a 2-week washout period before the start or resumption of AG-120 treatment. For subjects randomized to placebo who receive palliative radiotherapy before crossing over to AG-120, a repeat CT or MRI will be performed at the end of the 2-week washout period, which will serve as the new baseline for comparison for all subsequent scans in order to assess PFS2 (see Section 12.12.1). For subjects permitted to continue on open-label AG-120 beyond documented radiographic progression, a new baseline imaging assessment will not be required and the imaging assessments will continue on the current schedule.

Primary Endpoint Results and Subsequent Study Unblinding: Once the primary endpoint of PFS (based on central radiology RECIST 1.1 assessment) is statistically analyzed, the Sponsor will communicate the topline aggregate results of the study via public disclosure, which will include participating study teams. Shortly after public disclosure of the topline aggregate results, the Sponsor will communicate to all sites that treatment assignments of all subjects will be

unblinded and will also inform sites which of the 2 following scenarios to pursue following unblinding.

If the primary endpoint is statistically positive, all ongoing subjects (AG-120 and placebo-treatment assigned subjects) will be given the opportunity to receive open-label AG-120 following unblinding. Unblinding will no longer be contingent upon documented radiographic disease progression. Subjects who were already receiving AG-120 may continue to receive AG-120 on the same assessment schedule. Subjects who were receiving placebo and continue to meet cross-over eligibility criteria will be given the opportunity to receive open-label AG-120. For subjects who cross over, placebo will not be counted as a prior line of therapy for the purpose of eligibility. If subjects cross over, they will follow the same assessment schedule as from C1D1. Prior to crossing over, these subjects will undergo a CT or MRI that will serve as the new baseline against which all subsequent RECIST v1.1 assessments will be performed. If the subject has undergone a recent CT or MRI (≤ 3 weeks prior to start of cross-over treatment), the scan does not need to be repeated. Palliative radiotherapy to treat symptomatic pre-existing or new non-target lesions (per RECIST v1.1) that cannot otherwise be medically managed will be permitted after unblinding has occurred. AG-120 should be held for the duration of palliative radiotherapy. A 2-week washout from completion of radiotherapy will be required prior to starting or resuming AG-120. For subjects receiving palliative radiotherapy prior to the first dose of open-label AG-120, a repeat CT or MRI will be performed upon completion of the 2-week washout period to document the area that was irradiated and to serve as the new baseline. All decisions to pursue palliative radiotherapy will require Sponsor and/or Medical Monitor approval.

If the primary endpoint is statistically negative, all ongoing AG-120 subjects will be permitted to continue receiving open-label AG-120 following unblinding at the discretion of the treating investigator. Palliative radiotherapy will be allowed for subjects who continue receiving AG-120 as described in the preceding “statistically positive” paragraph. Subjects who were receiving placebo will not be permitted to receive open-label AG-120 in this scenario and will come off study.

9.7. Study Treatment Preparation and Administration

Daily treatment with AG-120 or placebo will begin on C1D1; clinical observations will be conducted over 4 hours following the first dose of study treatment on C1D1. Dosing is continuous; there are no planned inter-cycle rest periods. Subjects should be instructed to take their QD dose at approximately the same time each day.

Subjects should be instructed to swallow tablets whole and to not chew the tablets. Subjects may take AG-120 or placebo tablets with or without food. Subjects should be advised that if AG-120/placebo tablets are taken with food, the subject should avoid grapefruit or grapefruit products and avoid consuming a high-fat meal. Please refer to examples of low-fat and high-fat meals in Appendix 15.7.

If the subject forgets to take the daily dose, then they should take AG-120 or placebo within 12 hours after the missed dose. If more than 12 hours have elapsed, then that dose should be omitted, and the subject should resume treatment with the next scheduled dose.

Subjects will continue to receive best supportive care throughout the study, regardless of treatment arm.

Subjects may continue with their assigned study treatment until disease progression, development of unacceptable toxicity, confirmed pregnancy, death, withdrawal of consent, the subject is lost to follow-up, or the Sponsor unblinds or ends the study, whichever occurs first. Subjects who are determined to be on AG-120 upon study unblinding may continue on AG-120. For subjects who are determined to be on AG-120 upon radiographic disease progression and have demonstrated clinical benefit, PIs, with consult from the Sponsor, may keep the subjects on AG-120 after the disease progression. (See Section 9.6 for additional unblinding scenarios.)

9.8. Criteria for Dose Modification, Discontinuation of Study Treatment, Continuation Beyond Radiographic Progression, and Allowance of Palliative Radiotherapy

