9.9. Guidelines for Management of QT Prolongation

The discussion of the emergency management of Torsades de pointes and its hemodynamic consequences is beyond the scope of this guideline.

Events of QTcF prolongation \geq Grade 2 should be reported as AEs of special interest (AESIs) to the Sponsor within 24 hours, according to expedited reporting procedures (see Section 11.2.3).

The following are guidelines for the management of AEs of special interest based on the AG-120 non-clinical and clinical safety findings in subjects with solid tumors to date.

Prolongation of QTcF interval has been observed in monkeys at relatively high doses of AG-120 (see Section 5.3.2.2) and has been identified as an expected risk of treatment with AG-120 (see the Investigator's Brochure). As of 16 January 2016, 12 (10%) of 122 subjects in Study AG120-C-002 and 19 (16%) of 119 subjects in Study AG120-C-001 have experienced QT prolongation while receiving AG-120.

Subjects may be at increased risk for the development of QT prolongation when treated with AG-120 in combination with fluoroquinolones, azole antifungal agents, or serotonin (5-HT₃) antagonists. Investigators need to be vigilant; refrain from administering concomitant medications associated with QT prolongation and if no other therapeutic options are available, monitor subjects receiving study treatment with the combination of these drugs, and evaluate ECG and electrolytes (including potassium, magnesium, and calcium) particularly in subjects presenting with nausea, vomiting, or diarrhea. Systemic administration of a moderate or strong CYP3A4 inhibitor requires careful monitoring of QTcF (see Section 9.13.2).

Subjects who experience prolongation of the QTcF interval to >480 msec (CTCAE Grade ≥ 2) while receiving study treatment, should be promptly evaluated for causality of the QTcF prolongation and managed according to the following guidelines and Table 2:

- Levels of electrolytes (potassium, calcium, and magnesium) should be checked and supplementation given to correct any values outside the normal range.
- Concomitant therapies should be reviewed and adjusted as appropriate for medications with known QT prolonging effects.

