9.13.2. Concomitant Therapy Requiring Careful Monitoring

Concomitant use of drugs with a potential QT prolongation should be avoided and replaced with alternative treatments. If this is not possible, subjects receiving these drugs should be adequately monitored.

These medications include but are not limited to:

- Fluoroquinolones such as ciprofloxacin and moxifloxacin
- Azole antifungals such as fluconazole and posaconazole
- Serotonin (5-HT₃) antagonists such as granisetron and ondansetron

Other examples of drugs known to prolong the QT interval are listed in Appendix 15.5.

Systemic administration of moderate or strong CYP3A4 inhibitors (Appendix 15.6) requires careful monitoring of the QTc (see Section 9.13.4).

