9.13.4. Drug-Drug Interactions

AG-120 is mainly metabolized by CYP3A4 and, therefore, subjects should not use strong CYP3A4 inducers (Appendix 15.2) during treatment with AG-120.

AG-120 clinical trials and physiologically based pharmacokinetic (PBPK) simulations have shown that AG-120 plasma concentrations increase with co-administration of a strong or moderate CYP3A4 inhibitor, and increased AG-120 plasma concentrations may increase the risk of QTc prolongation. Therefore, alternative therapies that are not strong or moderate CYP3A4 inhibitors should be considered during treatment with AG-120. If concomitant use of strong or moderate CYP3A4 inhibitors is unavoidable, subjects should be monitored for increased risk of QTc prolongation.

AG-120 is an inducer of human CYP3A4/5 and may also induce CYP2B6, CYP2C8, and CYP2C9. Therefore, medications of sensitive CYP3A4 substrates with a narrow therapeutic window (Appendix 15.2) should be avoided unless the subject can be transferred to other medications prior to enrolling. Consider alternative therapies that are not sensitive substrates of CYP2C9 (eg, phenytoin, warfarin). Monitor international normalized ratio (INR) levels more frequently in subjects receiving warfarin (a CYP2C9 substrate) during initiation or discontinuation of AG-120.

AG-120 is an inhibitor of OAT3. A PBPK simulation predicted an increase (<30%) in the AUC of a sensitive OAT3 substrate, suggesting that the potential for clinically relevant drug interactions due to the inhibition of OAT3 appears to be low.

Coadministration of AG-120 may decrease the concentrations of hormonal contraceptives.

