15.6. Examples of Strong and Moderate CYP3A4 Inhibitors

Moderate CYP3A4 Inhibitors
Aprepitant, cimetidine, ciprofloxacin, clotrimazole, crizotinib, cyclosporine, dronedarone, erythromycin, fluconazole, fluvoxamine, imatinib, tofisopam, verapamil
Strong CYP3A4 Inhibitors
Boceprevir, clarithromycin, conivaptan, grapefruit juice, indinavir, itraconazole
Ketoconazole, lopinavir/ritonavir, mibefradil, nefazodone, nelfinavir, posaconazole
Ritonavir, saquinavir, telaprevir, telithromycin, voriconazole

Note: Based on FDA guidelines; Investigators should follow local institutional guidelines, where appropriate.

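### Section 9.7 makes its grapefruit advice depend on taking tablets with food, a condition that does not fit a listed strong CYP3A4 inhibitor

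*Protocol*

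**What the plan says.** Protocol Section 9.7 first sets the general rule: "Subjects may take AG-120 or placebo tablets with or without food". It then says what subjects are to be told: "if AG-120/placebo tablets are taken with food, the subject should avoid grapefruit or grapefruit products and avoid consuming a high-fat meal". It points to Appendix 15.7 for sample meals. Grapefruit and the high-fat meal share one clause and one condition.

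Grapefruit is named in only one other place. Appendix 15.6 has it in its strong CYP3A4 inhibitor list: "Boceprevir, clarithromycin, conivaptan, grapefruit juice, indinavir, itraconazole".

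Three sections set rules for that class of inhibitor:

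- Section 9.9: "Systemic administration of a moderate or strong CYP3A4 inhibitor requires careful monitoring of QTcF".
- Section 9.13.2, which cites Appendix 15.6: "Systemic administration of moderate or strong CYP3A4 inhibitors (Appendix 15.6) requires careful monitoring of the QTc".
- Section 9.13.4: "alternative therapies that are not strong or moderate CYP3A4 inhibitors should be considered during treatment with AG-120". If use cannot be avoided, subjects are to be monitored for QTc prolongation. The reason given is that "AG-120 plasma concentrations increase with co-administration of a strong or moderate CYP3A4 inhibitor", which may raise the QTc risk.

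None of the three mentions whether a dose is taken with food.

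**The concern.** A high-fat meal matters to dosing when the tablet is taken with that meal, so a meal condition is natural there. The protocol's reason for caution about CYP3A4 inhibitors is different. AG-120 is cleared mainly by CYP3A4, inhibitors raise its concentrations, and higher concentrations may prolong QTc. That reasoning does not depend on whether the tablet was swallowed with a meal. Putting grapefruit in the food sentence gives it a condition that belongs to the other item.

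What is at stake is a small point of subject safety. Section 5.4 names QT prolongation as the one expected risk of AG-120 in patients with solid tumors. Advice to subjects can prevent an exposure increase, whereas ECG monitoring finds QT prolongation after it has occurred.

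**Working it through.** There is no planned figure to reproduce and no calculation to run. The check is to set the statements side by side and see what each covers.

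| Place in protocol | What it asks | Condition | Names grapefruit? |
|---|---|---|---|
| Section 9.7 | Avoid grapefruit and a high-fat meal | Tablets taken with food | Yes |
| Appendix 15.6 | Classifies grapefruit juice as a strong CYP3A4 inhibitor | None | Yes (juice) |
| Section 9.13.4 | Consider alternatives; monitor QTc if unavoidable | During AG-120 treatment | No |
| Section 9.13.2 | Careful QTc monitoring | Systemic administration | Only through Appendix 15.6 |
| Section 9.9 | Careful QTcF monitoring | Systemic administration | No |
| Appendix 15.2 | Bars listed medicines and unspecified foods | While receiving study drug | No |

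1. *What Section 9.7 covers.* Grapefruit is itself a food, so swallowing tablets with grapefruit counts as dosing with food and the advice applies. It does not state that grapefruit is to be avoided by a subject who doses fasted, or at times of day away from a fed dose. The second gap applies equally to subjects who take their tablets with meals.

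2. *Whether time away from the dose matters.* Section 5.3.3.1 gives a mean half-life of 38.4 to 86.2 hours, and dosing is once every 24 hours. Since 38.4 / 24 = 1.6 and 86.2 / 24 is about 3.6, the half-life spans 1.6 to 3.6 dosing intervals. The drug is therefore present all day, whatever the subject ate with the tablet. This does not show how large a grapefruit effect would be. It shows only that the mealtime condition does not follow the drug's presence.

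3. *Whether another section closes the gap.* Appendix 15.2 refers to foods, but its two columns hold strong CYP3A inducers and CYP3A substrates with a narrow therapeutic window, and grapefruit is in neither. Section 9.13.2 brings in the Appendix 15.6 list, but its action is QTc monitoring, not advice to the subject. Section 9.13.4 speaks of therapies and asks only that alternatives be considered. No statement in the protocol or SAP tells subjects, without a food condition, to avoid grapefruit.

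**The case against.** The strongest reply is that the plan already deals with this. Section 9.13.2 adopts a list that names grapefruit juice, so sites can fairly read the inhibitor rules as covering it. ECGs are scheduled through Cycles 1 and 2, on Day 1 of every later cycle, at end of treatment and at safety follow-up (Section 10.5.4). QTcF above 480 msec triggers evaluation and dose management whatever the cause (Section 9.9, Table 2). All of this stands and limits the point. It does not supply the missing advice, and the references to systemic administration and to therapies leave room to read those rules as being about medicines.

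A second reply is that the effect may be small. Section 5.3.2.1 reports that itraconazole, also on the strong-inhibitor list, left AG-120 Cmax unchanged. Section 5.3.3.1 found no rise with dose in the common adverse events, QT prolongation among them. Section 7.3 describes exposure nearing a plateau at 500 mg. These are fair cautions against claiming harm. But the itraconazole result concerns Cmax only and is used there to judge intestinal P-gp, while Section 9.13.4 states that concentrations do rise with such inhibitors. The other two findings concern increasing dose, not inhibited metabolism.

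A reader might infer that a site following Section 9.7 to the letter would leave grapefruit out when advising a subject who doses fasted. The text does not support that. The duty to advise covers all subjects, and only the content of the advice is conditional.

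**Conclusion.** The point holds as a minor safety wording correction: the food condition in Section 9.7 fits the high-fat meal and not grapefruit. All subjects should receive the sentence, but as worded it leaves grapefruit unaddressed for fasted dosing and for other times of day. Existing monitoring mitigates this in part.

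The size cannot be calculated. The documents give neither a grapefruit effect on AG-120 exposure nor the number of subjects who would consume it. A reader might take the Phase 1 QT prolongation rates in Section 9.9 as a measure of the risk, but those rates are not linked to grapefruit and show no excess from it. Nor does the text permit grapefruit with fasted dosing; it is silent.

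The conclusion rests on the protocol's own classification of grapefruit juice and its stated reason for caution with CYP3A4 inhibitors. It concerns only what the protocol tells sites to advise. The home-administration instructions mentioned in Section 9.12 are not among the documents and may already be correct. Efficacy, alpha and power are unaffected.

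**What to change.** Split the sentence in Section 9.7 so that each item has its own condition:

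*Subjects should be advised to avoid grapefruit and grapefruit products throughout study treatment (see Section 9.13.4 and Appendix 15.6). If tablets are taken with food, subjects should avoid a high-fat meal (see Appendix 15.7).*

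Then check that the home-administration instructions say the same.

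The cost is one edited sentence with cross-references and that check. Visits, ECGs, data collection and analysis do not change. The downside is a slightly broader dietary restriction. Its wording is also firmer than Section 9.13.4 uses for inhibitor medicines, although it is no firmer than Section 9.7 already is about grapefruit with a fed dose.

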9.8.1. Study Treatment Dose Modification and Stopping Criteria

9.8.1.1. Dose Modifications and Delays

For any AE, including AEs not specifically mentioned in Table 1, the Investigator may decide to delay dosing or modify the dose of AG-120/placebo based on clinical judgment. These decisions should be discussed with the Medical Monitor prior to implementation. Dose modifications of AG-120/placebo from 500 mg to 250 mg will be permitted on study for management of AEs (Table 1). If more than one AE occurs that would require a dose modification, upon resolution of all AEs to baseline or Grade 1, AG-120/placebo should be dose reduced to 250 mg. Re-escalation may be allowed with approval from the Medical Monitor.

Dose delays are discouraged, except as needed for management of AEs, dose holds during palliative radiotherapy, and washout from palliative radiotherapy. Dose delays up to 28 days will be permitted at the discretion of the Investigator in consultation with the Medical Monitor for reasons including management of AEs and for mitigating circumstances (eg, planned procedures). Palliative radiotherapy delivered in the unblinded open-label cross over period or in the setting of continuation of AG-120 beyond disease progression will require a 2-week washout period after radiotherapy before the resumption of AG-120 treatment (see Section 9.8.1.3). Palliative biliary decompression procedures will be permitted on study and will not require interruption of AG-120/placebo.

If the subject cannot resume AG-120/placebo within 28 days, the subject should be discontinued from study medication. Other reasons for treatment termination are provided in Section 8.5. If AG-120 or placebo is discontinued, the subject will complete the EOT and Follow-up Visits, and then enter PFS follow-up (if disease has not progressed) and survival follow-up. Exemptions may be considered for those subjects who are determined by the Investigator to have received clinical benefit from treatment. If a dose is delayed for the management of an AE, the subject should resume the study at the next planned visit within a dosing cycle (eg, if the subject did not start dosing at C3D1 due to management of an AE, then dosing would be resumed at C3D1 upon resolution of the AE, not C3D15).

Table 1: Management of Adverse Events

Adverse Events	Action
Grade 2 nausea or vomiting (related or unrelated)	
 • Consider holding dose of AG-120/placebo until resolution of AE to Grade ≤ 1 within 28 days of supportive therapy. • Manage with supportive therapy according to the institutional standard of care. • May resume AG120/placebo at same dose.
Grade 3 adverse events (related, first event)	
 • Hold dose of AG-120/placebo until resolution to Grade ≤ 1 or baseline within 28 days of supportive therapy and then resume dose. • Manage with supportive therapy according to the institutional standard of care. • If the Grade 3 AE recurs (a second time), consider reducing AG-120/placebo to 250 mg in consultation with the Medical Monitor. Re-escalation may be permitted after discussion with the Medical Monitor. • If the Grade 3 AE recurs (a third time) despite dose reduction of AG-120/placebo, then consider discontinuing AG-120/placebo in consultation with the Medical Monitor.
Grade 4 adverse events (related, first event)	
 • Hold AG-120/placebo. • Manage with supportive therapy according to the institutional standard of care. • If the AE resolves to Grade ≤ 1 or baseline within 28 days, then restart AG-120/placebo dosing at 250 mg in consultation with the Medical Monitor. • If the AE does not resolve to Grade ≤ 1 or baseline within 28 days, consider discontinuing study treatment in consultation with the Medical Monitor. • If the Grade 4 AE recurs (a second time), despite dose reduction, AG-120/placebo should be discontinued in consultation with the Medical Monitor.

*See Table 2 for specific dose modifications for QTcF prolongation.

